2. REGISTRY OVERVIEW

2.1 Registry Design

The PROCLAIMSM Registry is a US-based, multicenter Registry designed to establish a high quality observational database of real-world clinical data on HD IL-2 when used to treat patients with mRCC, mM or other malignancies. The Registry will not, in any way, suggest changes in the treatment or management of the patients enrolled in the Registry. Therefore, physicians will continue to manage and treat patients according to standard of care and their own judgment.

The PROCLAIMSM Registry will start with a retrospective pilot data collection from a de-identified finite number of patient cases abstracted from their existing medical charts. The features collected will be identical to those planned for the prospective registry. The resulting database will be used to formulate hypotheses to be tested using the prospective registry database. Patients utilized in the retrospective analysis will be excluded from the prospective portion of the PROCLAIMSM Registry.

In the prospective portion of the Registry, sites will enroll patients who are expected to start a course of HD IL-2 therapy or have not yet completed their 1st course of HD IL-2

treatment. Once enrolled, the patient must receive at least one dose of HD IL-2 to remain in the Registry. Patients will be treated and followed according to the site's standard of care. This Registry will in no way induce changes in the management of individual patients. Clinical data features will be entered into an Electronic Data Capture (EDC) system, and organized into a registry database. The registry database will be interrogated according to database query protocols approved by the Steering Committee. (See **Appendix A** for an example data query proposal to the Registry Database). A subset of patients will participate in one of the Prometheus Proclivity studies (12PLK01, 12PLK02, 12PLK03). The Proclivity studies involve HD IL-2 in sequence with another therapy. Patients enrolled into any of the Proclivity studies and received a least one dose of HD IL-2 will be enrolled and followed in the Proclaim registry.

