4. REGISTRY PLAN

4.1 Investigator Site Selection Criteria

Investigator sites will be included based on feasibility analysis of established medical centers where patients are treated with HD IL-2 by qualified physicians. Additional data on site characteristics, standard treatment approach, and volume of patients treated will be assessed. An adequate blend of high volume sites (sites that treat a minimum of 25 HD IL-2 patients per year) and low volume sites (sites that treat 5-15 HD IL-2 patients per year) as well as a representative distribution of patients with mM and mRCC, will be needed to participate in the Registry. Once sites are selected to participate in the Registry, the site physicians will enroll patients into the Registry. Treatment and follow up will occur per the site's standard of care.

The Registry is planned to include 25 sites in the US for prospective patient entry. Once the Registry procedures are established, additional sites may be added. Of the initial 25 planned sites, approximately 10 will apply the registry data collection instruments retrospectively to their HD IL-2 patients from several previous years, as a test of the system, and to create a separate database.

For retrospective participation, a site must have treated approximately 25 HD IL-2 patients in the previous year prior to participation in the Registry and have a medical record database that allows efficient retrospective data extraction (e.g., a qualified EMR system or research database). The PROCLAIMSM Registry will adjust the starting date for retrospective data collection to accrue an average of 25 consecutive patients at each site.

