4.5 Patient Inclusion/Exclusion Criteria

4.5.1 Inclusion Criteria

Patients who meet all of the following criteria will be eligible for inclusion into the Registry:

Prospective Cohort:

- 18 years of age and older
 - Given informed consent for participating in the Registry
- Is receiving or has received an initial course (2 cycles) of HD IL-2 and has not had post treatment imaging studies performed prior to enrollment. Data will only be collected and analyzed for patients who received at least one dose of HD IL-2. Exception: Patients enrolled in a Proclivity study (12PLK01, 12PLK02 or 12PLK03) can be enrolled into the registry at anytime.

Retrospective Cohort:

- 18 years of age and older
- Received HD IL-2 at the site prior to site initiation
- Have conformed to site specific guidelines permitting research on medical records without personal identification

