4.5.2 Exclusion criteria

Patients who meet the following criteria will be excluded from participation in the Registry:

Prospective Cohort:

- Received more than 1 course of HD IL-2 as defined in 4.5.1

Retrospective Cohort:

- Treatment with HD IL-2 occurring more than 5 years ago

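### The retrospective cohort has no first-course limit and no anchor for its consecutive patients, so it may not be comparable with the prospective cohort that tests its hypotheses

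*Protocol*

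**What the plan says.** **Retrospective cohort.** Section 4.5.1 requires age 18 or over, compliance with the site's rules on records research, and that the patient "Received HD IL-2 at the site prior to site initiation". The only exclusion in 4.5.2 is "Treatment with HD IL-2 occurring more than 5 years ago". Section 4.1 says the registry will "adjust the starting date for retrospective data collection to accrue an average of 25 consecutive patients at each site", at approximately 10 sites.

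**Prospective cohort.** Section 4.5.1 requires that the patient "Is receiving or has received an initial course (2 cycles) of HD IL-2 and has not had post treatment imaging studies performed prior to enrollment". Section 4.5.2 excludes anyone who "Received more than 1 course of HD IL-2 as defined in 4.5.1". There is one exception: Proclivity patients "can be enrolled into the registry at anytime".

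**Link between the two.** Section 2.1 says of the retrospective data: "The resulting database will be used to formulate hypotheses to be tested using the prospective registry database". Section 3.2 makes hypothesis generation a secondary objective.

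**Time origin.** Section 5.2 counts OS and PFS from initiation of HD IL-2 and does not say which course is meant when there has been more than one.

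**The concern.** The two cohorts are meant to work as a pair: one suggests hypotheses and the other tests them, using the same data features (2.1). Their entry rules differ in course number, and the protocol gives no reason.

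If a site finds its consecutive patients by looking for any HD IL-2 treatment in the window, it collects two kinds of patient. Some started in the window. Others started earlier, lived long enough to be treated again, and returned. Patients who started alongside the second group but died or stopped have no treatment in the window and are missed. This is prevalent-patient sampling.

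Returners probably include more patients who had not progressed, because 4.7.2 records best response and continuation of HD IL-2 at the same initial assessment. They also have more cycles, since a course is 2 cycles. If their survival is counted from first dose, it includes a period during which they could not have died and still been sampled. If the first course was given elsewhere, the site's chart may not hold the date of first dose.

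At stake is whether a pattern seen in the retrospective data carries over to the prospective cohort, or fails to replicate only because the populations differ.

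**Working it through.** **1. The protocol's own figure.** About 10 sites × an average of 25 patients = 250. This matches the approximately 250 in 4.2. The protocol gives no retreatment share and no retrospective outcome figure, so everything below rests on assumptions.

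**2. The entry rules side by side.**

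| | Retrospective | Prospective |
|---|---|---|
| Course number | not stated | initial course; more than 1 excluded |
| Look-back | 5 years | not applicable |
| Sampling | consecutive, event not stated | all eligible patients offered entry |
| Exception | none | Proclivity patients at any time |

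**3. Share of earlier starters.** Assumptions: 25 new patients a year per site; a share s2 has a second course at about 3 months and a share s3 a third at about 6 months; any treatment in the window qualifies. Second-course returners started in the quarter-year before the window. Third-course returners not already counted started in the quarter-year before that.

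Earlier starters = 25 × 0.25 × (s2 + s3)

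| s2 / s3 | Earlier starters | Share, one-year window (25 new) | Share, three-year window (75 new) |
|---|---|---|---|
| 20% / 5% | 1.56 | 1.56/26.56 = 5.9% | 1.56/76.56 = 2.0% |
| 40% / 15% | 3.44 | 3.44/28.44 = 12.1% | 3.44/78.44 = 4.4% |
| 50% / 25% | 4.69 | 4.69/29.69 = 15.8% | 4.69/79.69 = 5.9% |

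The share does not depend on the assumed 25 a year, because numerator and denominator scale together. Both windows are plausible. Section 4.1 asks for about 25 patients treated in the previous year and about 25 accrued, which suggests one year, but it also speaks of several previous years. In a cohort of 250, 12.1% is about 30 patients and 4.4% about 11.

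**4. Survival, if counted from first dose.** Assumptions: exponential OS with true median m and λ = ln 2 / m; a share f was certain to survive g months. The survival curve beyond g is e^(−λt) × (1 − f + f·e^(λg)), so for medians beyond g:

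Apparent median = m + ln(1 − f + f·e^(λg)) / λ

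The values of m are 8.8 months (top of the melanoma range in 1.1) and 17.5 months (midpoint of 16-19 for RCC in 1.1).

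| f, g | m = 8.8 | m = 17.5 |
|---|---|---|
| 5%, 3 months | 8.97 | 17.66 |
| 10%, 3 months | 9.13 | 17.82 |
| 10%, 6 months | 9.54 | 18.17 |
| 20%, 6 months | 10.25 | 18.82 |
| 30%, 12 months | 13.71 | 21.73 |

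The last row goes beyond the shares and return times in step 3 and shows an extreme. For the central share (12.1%, returns at 3-6 months), the 10% rows are closest: a shift of about 0.3 to 0.7 months. With f = 0 there is no shift. If the clock starts at the later course, this guaranteed time disappears and the protocol does not determine the direction of any difference.

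**The case against.** The strongest reply is that 4.1 can be read as consecutive treatment starts. On that reading no earlier starter enters and there is no bias. The reading is reasonable, but the text does not require it, and 4.5.1 asks only for treatment at the site. The ambiguity therefore stands.

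Three further objections hold in part:

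- **The 5-year exclusion.** A reader might infer that anyone ever treated can enter. That is not so: on a plain reading, a course more than 5 years old excludes the patient. It does not exclude patients who return after 3 to 6 months.
- **The comparator is not purely first-course.** Proclivity patients may join the prospective cohort at any time. They are a subset (2.1), and the exclusion in 4.5.2 states no exception for them, so the contrast is weakened but not removed.
- **Analysis could repair it.** The features are to be identical across cohorts. They include history and dosing by cycle (4.7.2), and Appendix A lists the first-dose date. A query could then drop retreated patients or allow for delayed entry. This depends on the first-dose date being captured, and it cannot refill the places those patients took.

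The limit on the consequence stands in full. Section 4.1 describes a test of the system and a separate database, and the Appendix A query takes prospective patients only.

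**Conclusion.** The point holds as a defect of comparability. The retrospective rules allow patients selected for surviving to a later course, and the prospective rules largely do not. The retrospective cohort is probably the more favourable on response, cycles per patient and survival from first dose. Earlier starters might be 6-16% of a one-year window or about 4% of a three-year window, on the assumed retreatment shares and on capture by any treatment in the window.

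Stronger readings are not supported:

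- A reader might infer that the retrospective figures are shown to be too favourable. They are not: the protocol gives no retreated share and does not tie the OS and PFS clock to a course.
- A response-rate distortion cannot be given reliably. Taking ORR as 20% in all new patients and 50% in retreated ones, with 40% retreated, makes retreated responders 0.40 × 0.50 = 20% of all patients. That requires every responder to be retreated.
- Treatment emergent mortality has no determined direction, because it depends on mortality in later courses.
- The planned sample size is not affected. Appendix A section 8.1 uses historical death rates of 2% and 4% and an expected 1%, not retrospective data.

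This should be corrected before chart abstraction starts, but it does not threaten the registry's main use.

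**What to change.** In 4.1 and 4.5.1, define the retrospective cohort as consecutive patients by date of first HD IL-2 dose, with that date inside the sampling window. Record later courses of these patients as follow-up. State in 5.2 that OS and PFS run from that first dose.

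If patients with an earlier course, before the window or elsewhere, are to be kept in order to describe care patterns, record course number and date of first dose. Analyse them separately or with delayed entry.

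The cost is a few lines of wording and a slightly earlier start date, which 4.1 already allows to move. Replacing 3.44 patients at 25 a year takes 3.44/25 × 12 = 1.65 months per site. The low and high cases give 1.56/25 × 12 = 0.75 and 4.69/25 × 12 = 2.25 months.

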4.5.2 Exclusion criteria

Patients who meet the following criteria will be excluded from participation in the Registry:

Prospective Cohort:

- Received more than 1 course of HD IL-2 as defined in 4.5.1

Retrospective Cohort:

- Treatment with HD IL-2 occurring more than 5 years ago

4.6 Participant Withdrawal

At any time a patient may request that his or her data no longer be available for research purposes. Instructions on how to withdraw consent will be provided in site specific informed consent documents.

4.7 Data Collection Strategies

Data will be collected for this registry database using an electronic data capture (EDC) platform. Site staff will use an electronic case report form (eCRF) to enter specific clinical data of interest into the registry database. All data submitted into the registry database must have corresponding source documentation (medical records or management charts, physician notes, etc). Preliminary retrospective data or any other data needed for the study may be collected on paper CRFs and entered into the EDC database by the sponsor or the sponsor's delegate.

4.7.1 Collection of Site Specific Data

Data pertinent to site specific practices on HD IL-2 administration will be collected from each participating site using a set of standard CRFs. Site staff are responsible for submitting these data to the registry database at the time of site initiation.

4.7.2 Collection of Patient Data

Pre-specified standard patient data will be collected at the time a patient joins the Registry, at each cycle of HD IL-2 therapy, at the standard initial tumor assessment (usually it's approximately 3-months after the beginning of HD IL-2 therapy), and at the standard interval follow-up visits (approximately every 6-months). All these data should be abstracted from the patient's medical records maintained at the treatment site. The registry database will be

available for future data queries approved by the PROCLAIMSM Registry Steering Committee.

Standard of Care Visits	Data to Collect ^a
Baseline Assessment	Informed Consent Inclusion/exclusion criteria Demographics and relevant history
HD IL-2 Treatment – For Each Cycle	Relevant laboratory results Dosing information, including reasons for discontinuation Concomitantly administered anti-tumor therapy
Initial Treatment Assessment	Best overall response determined by clinician Continuation of HD IL-2 therapy
Post-Treatment Follow-ups – For Each Interval Visit	Autoimmune disease (+/-) Disease response since last assessment, determined by clinician Interval therapy history Survival status Note: If the patient is not able to have an in office follow-up visit, the information can be collected via phone.

^a Only de-identified data will be collected on retrospective patients.

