5.1 Tumor Assessments and Response

The tumor responses to HD IL-2 treatment will be determined by the site PI. Tumor responses will be assessed and categorized as CR, PR, SD, or PD using either RECIST or WHO criteria per site's standard procedure*. The sites will be required to indicate which criteria were employed in each patient's tumor assessments.

* PET scan may be used to confirm a CR or a conversion of a PR to a CR. There may also be surgical conversion of a PR to a CR. The site staff will adequately document these conversion cases on the case report forms for inclusion in the database.

Best Overall Response (BOR):

BOR is defined in this Registry as the investigator determined best response, occurring at or prior to Month 3; if the BOR is CR, PR, or SD, response since the last evaluation and TTP (first progression after Proleukin will be evaluated at standard of care interval visits (approximately every 6 months) until disease progression.

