5.2 Patient Survival

Overall Survival (OS):

The OS is defined as the time from initiation of HD IL-2 treatment until patient death for any reason

Progression Free Survival (PFS):

PFS in this Registry is defined as the time from initiation of HD IL-2 treatment until disease progression or death.

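### The follow-up note lets disease response be collected by phone, although response must be categorised by the site PI with RECIST or WHO; undocumented calls may be entered as no progression and push TTP and PFS upward

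*Protocol*

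**What the plan says.** The data table in Protocol section 4.7.2 lists four items for each post-treatment interval visit: autoimmune disease, disease response, interval therapy and survival status. The response item reads "Disease response since last assessment, determined by clinician". The note beneath the items says "If the patient is not able to have an in office follow-up visit, the information can be collected via phone" and exempts none of them.

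Three other rules bear on the same data:

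- **Who judges response, and how (section 5.1).** "The tumor responses to HD IL-2 treatment will be determined by the site PI", and "Tumor responses will be assessed and categorized as CR, PR, SD, or PD using either RECIST or WHO criteria per site's standard procedure". For patients whose best response is CR, PR or SD, later response and first progression "will be evaluated at standard of care interval visits (approximately every 6 months) until disease progression". These are the contacts to which the phone note applies.
- **Where the data come from (sections 4.7.2 and 4.7).** "All these data should be abstracted from the patient's medical records maintained at the treatment site". Section 4.7 adds: "All data submitted into the registry database must have corresponding source documentation (medical records or management charts, physician notes, etc".
- **What the data feed (sections 5.2 and 6).** PFS is "the time from initiation of HD IL-2 treatment until disease progression or death", and section 6 puts PFS in the annual summary.

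The protocol does not say how a phone contact without a tumour assessment enters response, TTP or PFS.

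**The concern.** Survival status and interval therapy can be obtained by phone. A RECIST or WHO category cannot be obtained from a call alone. The note treats these items alike, so it permits by one route what section 5.1 requires by another. A site could ring a patient who feels well and enter no progression. The source rule would not necessarily stop this, because physician notes qualify and a charted call is such a note.

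If that happens and the patient has progressed without symptoms, progression is dated to a later contact. TTP, PFS and apparent durability of response then move upward. This matters here because section 3.1 makes a standardised source of outcome data the registry's primary objective. Section 1.1 presents lasting responses as the main attraction of the therapy and counts difficulty with follow-up among the weaknesses of earlier reports.

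OS, treatment emergent mortality and the 3-month ORR do not depend on the note.

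**Working it through.** No figure in the protocol rests on this point. The only sample size, in Appendix A section 8.1, is for treatment emergent mortality. The check is a comparison of the passages, followed by an illustration of size.

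**Comparison.** The phone note (4.7.2) covers disease response. Section 5.1 requires a site-PI category by RECIST or WHO and assigns follow-up of response and first progression to the same interval visits. The note can be reconciled with 5.1 only if the call relays an assessment already made, which the clinician then judges. The note does not say so.

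**Inputs.** The interval of about 6 months is from section 5.1, and the first assessment at about 3 months is from section 4.7.2. Three inputs are not in the protocol and are assumed: phone share f, from 10% to 50%; probability u that a phone contact misses an existing progression, 0.5 or 1; and true median PFS, 4, 6 or 12 months.

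**Mean delay.** If contacts are independent, each misses an existing progression with probability g = f × u. The number of consecutive misses is geometric with mean g/(1−g), so the mean extra delay for a progression after month 3 is 6g/(1−g) months.

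| f | all missed (u = 1) | half missed (u = 0.5) |
|---|---|---|
| 10% | 6×0.10/0.90 = 0.67 | 6×0.05/0.95 = 0.32 |
| 20% | 6×0.20/0.80 = 1.50 | 6×0.10/0.90 = 0.67 |
| 30% | 6×0.30/0.70 = 2.57 | 6×0.15/0.85 = 1.06 |

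The u = 1 column is the upper bound. The formula also ignores death, which is itself a PFS event and would cut some delays short.

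**Recorded PFS at 12 months.** Take exponential progression times, S(t) = 2^(−t/median), with assessments at months 3, 9, 15 and so on, and only those after month 3 possibly by phone. Recorded 12-month PFS is S(9) with no phone contacts and S(9) + f·u·[S(3) − S(9)] with them. For a median of 6 months, S(3) = 70.7% and S(9) = 35.4%. At f = 20% this gives:

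- u = 0.5: 35.4 + 0.10 × 35.4 = 38.9%
- u = 1: 35.4 + 0.20 × 35.4 = 42.4%

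A simulation of the same set-up gave 38.8% and 42.4%.

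The rise f·u·[S(3) − S(9)] in percentage points, from u = 0.5 to u = 1:

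| Median (months) | S(3) − S(9) | f = 10% | f = 20% | f = 50% |
|---|---|---|---|---|
| 4 | 59.5 − 21.0 = 38.4 (from unrounded values) | 1.9–3.8 | 3.8–7.7 | 9.6–19.2 |
| 6 | 70.7 − 35.4 = 35.4 (from unrounded values) | 1.8–3.5 | 3.5–7.1 | 8.8–17.7 |
| 12 | 84.1 − 59.5 = 24.6 | 1.2–2.5 | 2.5–4.9 | 6.2–12.3 |

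The rise is zero if u = 0, or if contacts without an assessment are not counted as progression-free assessments. The timing error from 6-monthly assessment is present with or without phone contacts and is not part of these figures.

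**The case against.** The strongest reply is that the note describes how information is gathered, not how tumours are assessed. The item is still the clinician's determination, section 5.1 still applies, and a call may relay a scan done elsewhere or reveal clinical progression in a patient otherwise lost to follow-up. An unassessed response can be left missing. All of this is fair, and it means the bias is a risk and not an established fact. It does not remove the conflict, because the note as worded neither limits phone collection to relayed assessments nor exempts response.

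A reader might also infer that phone entries could never be told apart from assessed ones. The protocol does not support that. Section 5.1 requires sites to state the criteria used for each patient's assessments, and Appendix A section 7.4 lists how response was assessed among the features for analysis. The eCRF is not shown, so the absence of an assessment date or a 'not assessed' option in the 4.7.2 table does not prove that the form lacks them.

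The conflict with record abstraction is weaker than the one with section 5.1, since a charted call is part of the record. Heavier phone use among distant patients is plausible, but the protocol says nothing about it.

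Finally, the rule for censoring PFS is ordinary analysis-plan content, and its absence from the protocol is not a fault. What may be collected by phone is a data-collection rule, and the protocol itself fixes it.

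**Conclusion.** The point holds as a conflict between the phone note in section 4.7.2 and the assessment rule in section 5.1, with a plausible upward bias in TTP and PFS. A reader might go further and conclude that unscanned progression is recorded as progression-free and that PFS is therefore overstated. The protocol contains no such recording rule, so that conclusion is not supported.

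The size cannot be determined from the protocol. Mean delays of 0.7, 1.5 and 2.6 months at 10%, 20% and 30% phone contacts are upper bounds that assume every phone contact misses an existing progression. Under the assumed medians, 12-month PFS would rise by about 1 to 4 percentage points at 10% phone contacts and about 6 to 19 at 50%, if half to all progressions are missed and the contacts count as progression-free.

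The consequence is moderate. PFS is an annual descriptive output in a registry that mandates no visits; it is neither the registry's primary objective nor the primary endpoint of the Appendix A query. The wording should still be corrected, because the change is small and protects an outcome that the registry reports every year.

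**What to change.** Reword the note in section 4.7.2 along these lines:

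> Survival status, interval therapy and autoimmune disease may be collected by phone. Disease response and progression are entered only from a tumour assessment documented in the record, with its date, including outside reports obtained after a call. Where there is none, enter 'not assessed'.

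State in section 5.1 or 5.2 that a contact without a tumour assessment does not count as a progression-free assessment, and leave the detailed censoring rule to the analysis plan. Confirm that the follow-up eCRF has an assessment date and a 'not assessed' option, and add them if it does not.

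The cost is protocol wording and possibly two eCRF fields. There will be more 'not assessed' entries, some patients will be censored earlier, and PFS will be slightly less precise. No visit or scan is added, so the registry stays observational as section 2.1 requires. The timing error from 6-monthly assessment remains.
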